5.2 Randomization

Randomization will be performed by the Department of Biostatistics

6.0 Treatment Program

6.1 Treatment Overview

Treatment will be administered in an outpatient setting.

6.1.1 Schedule

In patients on the experimental arm, axitinib should be taken at a dose of 5 mg oral bid, with 28 days of therapy constituting 1 cycle.

The date of initiation of axitinib therapy will be contingent upon the date selected for prostatectomy and pelvic lymph node dissection, with 28 days of planned therapy to conclude 48 hours prior to surgical intervention.

In patients on the control arm, no systemic therapy will be instituted. Rather, prostatectomy and pelvic lymph node dissection will be carried out within 5-6 weeks after biopsy confirmation of prostate cancer.

6.1.2 Criteria for Starting Subsequent Cycles

Only one cycle of axitinib (28 days of therapy) will be instituted in the current protocol.

6.2 Laboratory Studies

A local laboratory is to be used to perform all clinical laboratory assessments. Laboratory tests should be performed as indicated in the Time and Events Table(s). All laboratories prior to week 9 may be performed/collected within +/- 3 days of the dates specified in the study calendar. From week 9 onwards, all laboratories may be performed/collected within +/- 7 days of the dates specified in the study calendar. Assessments may be performed more frequently if clinically indicated.

All laboratory tests with values that become clinically abnormal while the subject is participating in the study or within 28 days after the last dose of study drug should be repeated until the values return to normal or baseline.

Results for all unscheduled clinical laboratory assessments (i.e., haematology, TSH/T₄, coagulation parameters) should be recorded on an unscheduled laboratory form in the eCRF.

Hematology and Clinical Chemistry

Hematology and clinical chemistry laboratory parameters that should be reported include white blood cell count, hemoglobin, hematocrit, platelet count, sodium, potassium, chloride, carbon dioxide, BUN, creatinine, and blood glucose. Assays for hematology and clinical chemistry should be performed according to the study calendar. Estimated creatinine clearance should be calculated using the Cockcroft and Gault method.

Liver Function Tests

When a separate liver function test (LFT) panel is conducted, this panel should include the following: ALT, AST, alkaline phosphatase, and total bilirubin. A direct bilirubin level should be obtained if the total bilirubin level is greater than 1.5 x upper limit of normal (ULN). Liver chemistry threshold stopping criteria and dose modification guidelines have been designed to ensure subject safety.

Evaluation of Proteinuria To be eligible for the current protocol, urinary protein must be <2+ by standard urine analysis (UA). If UA is $\geq 2+$ for protein then a 24-hour urine collection can be done and the patient may enter only if urinary protein is <2 g per 24 hours. Proteinuria will be evaluated using the urine protein to creatinine ratio (UPC; see Appendix B). .

Coagulation Tests

Coagulation tests should be performed as specified in the Time and Events Table and also in response to an AE/SAE as clinically indicated. Coagulation tests include activated partial thromboplastin time (aPTT), prothrombin time (PT) and international normalized ratio (INR).

Lipid Tests

Lipid tests include cholesterol, high-density lipoprotein (HDL), low-density lipoprotein (LDL), and triglycerides. These tests should be performed as specified in the Time and Events Table. Additional testing may be performed if clinically indicated. In such a case, the subject should be in a fasting state.

Thyroid Function Tests

Thyroid function tests to assess thyroid stimulating hormone (TSH) and thyroxine (free T₄) should be performed as specified in the Study Calendar. Unscheduled thyroid function tests (TSH and free T₄) may be performed if clinically indicated (e.g., if a subject develops signs and symptoms suggestive of hypothyroidism).

6.3 Studies Obtained During the Trial

Physical examination: to identify any changes in the subject's mental and medical conditions since baseline assessment that would make him ineligible for the study. This will occur as per the study calendar. Patients will then be evaluated in the clinic with a physical examination and examination for pertinent toxicities one month following prostatectomy (constituting a standard post-operative assessment), and then every 3 months, until evidence of disease progression, death, or initiation of a subsequent line of prostate cancer therapy.

ECOG PS: Per study calendar, section 10.0.

PSA will be performed per the study calendar, section 10.0, from randomization until the development of metastatic recurrence.

Blood will be sequestered for correlative studies (see section 10.1) at baseline and at the time of prostatectomy, as well as the post-prostatectomy follow-up visit 4 weeks following the procedure. A total of 20 mL of blood will be collected at each of these visits; 10 mL will be collected in a CPT tube for PBMC isolation and assessment, while 10 mL will be collected for assessment of selected plasma angiogenic factors. Within 4 hours of collection, this blood will be transported to the lab of [name] (Beckman Research Institute, Room 3220).

6.4 Post-Study Assessments

Any patient who is discontinued from study treatment for any reason other than progressive disease (PD) will continue to have PSA measurements every 24 weeks (+/- 2 weeks) until the patient starts another anticancer therapy. The investigator or his/her designee will continue collecting information on the initiation of anticancer therapies until the date of data cutoff for the final analysis. All new anticancer therapy therapies after the last dose of treatment will be recorded on the appropriate CRF.

6.5 Criteria for Removal from Study

Treatment may continue until one of the following criteria applies:

- Disease progression,
- Intercurrent illness that prevents further administration of treatment,
- Unacceptable adverse event(s),
- Patient decides to withdraw from the study,
- General or specific changes in the patient's condition render the patient unacceptable for further treatment in the judgment of the investigator, or
- Treatment delays of > 1 week due to adverse events.

Treatment may be interrupted for up to 1 week and missed doses should be omitted. However, patients will be replaced if they do not receive at least 75% of the planned treatment with axitinib in the first cycle of therapy, amounting to 21 days of treatment out of the planned 28 days of therapy.

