Proteinuria will be evaluated using the urine protein to creatinine ratio (UPC; see Appendix B). UPC will be determined at times specified in the Study Calendar.

Coagulation Tests

Coagulation tests should be performed as specified in the Study Calendar and also in response to an AE/SAE as clinically indicated. Coagulation tests include activated partial thromboplastin time (aPTT), prothrombin time (PT) and international normalized ratio (INR).

Lipid Tests

Lipid tests include cholesterol, high-density lipoprotein (HDL), low-density lipoprotein (LDL), and triglycerides. These tests should be performed as specified in the Study Calendar. Additional testing may be performed if clinically indicated. In such a case, the subject should be in a fasting state.

Thyroid Function Tests

Thyroid function tests to assess thyroid stimulating hormone (TSH) and thyroxine (free T₄) should be performed as specified in the Study Calendar. Unscheduled thyroid function tests (TSH and free T₄) may be performed if clinically indicated (e.g., if a subject develops signs and symptoms suggestive of hypothyroidism).

Statistical Considerations:

The primary endpoint of this study is pre-metastatic niche density, as defined by the average number of VEGFR1 clusters in 8 distinct 40x microscopic fields. We will use a two sample student's T-test to compare the primary endpoint of pre-metastatic niche density in the regional lymph nodes of patients treated with axitinib, as compared to the pre-metastatic niche density in the lymph nodes of patients enrolled on the control arm. With a sample of 22 patients per group, we will have 80% power to determine significance across groups if the average niche density is 3.13 in patients in the control arm, and at most 2.19 in patients treated with axitinib (a one-sided t-test with type I error = 10% calculated using nQuery Advisor 6.01).

Table of Contents

SECTION	PAGE
1.0 Goals and Objectives (Scientific Aims).....	13
1.1 Primary Objectives	13
1.2 Secondary Objectives	13
2.0 Background.....	13
2.1 Defining prognosis in prostate cancer.....	13
2.2 Personalizing prognostic models in prostate cancer: The pre-metastatic niche...	13
2.3 VEGFR1 ⁺ Bone Marrow Derived Cells (BMDCs) initiate the pre-metastatic niche.	14
2.4 Hypoxia-induced LOX recruits BMDCs to the pre-metastatic niche.	14
2.5 MDSC recruitment may represent an early event in pre-metastatic niche formation.	14

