14.0 Statistical Considerations

14.1 Study Design

14.1.1 The study is an open label, randomized phase II assessment of axitinib as pre-surgical therapy in high risk prostate cancer. In particular, a permuted block randomization scheme will be carried out to achieve treatment/control balance. To avoid selection bias, the blocking scheme will be masked to the principal investigator. The number of blocks will be determined by stratifying high risk patients according to PSA levels (≥ 20 or not) and Gleason scores (≥ 8 or not). For each block, we will randomly choose one arrangement from all possible realizations.*Primary Endpoints*: The primary endpoint of this study is pre-metastatic niche density, as defined by the average number of VEGFR1 clusters in 8 distinct 40x microscopic fields. We will use a two sample student's T-test to compare the primary endpoint of pre-metastatic niche density in the regional lymph nodes of patients treated with axitinib, as compared to the pre-metastatic niche density in the lymph nodes of patients enrolled on the control arm. With a sample of 22 patients per group, we will have 80% power to determine significance across groups if the average niche density is 3.13 in patients in the control arm, and at most 2.19 in patients treated with axitinib, with a common standard deviation 1.43 using a one-sided t-test assuming a type I error = 10% (Calculated using nQuery Advisor 6.01) Taking this into consideration, 30 patients per group will be recruited according to an empirical replacement rate of 27%. The intention-to-treat analysis will be the primary analysis conducted to obtain unbiased comparisons between the treatment and control. In addition, some as-treated subgroup analysis would also be investigated if necessary.*Secondary Endpoints*: Toxicity, time to biochemical recurrence, time to metastatic recurrence. With respect to secondary endpoints, Cox regression will be used (with the log-rank test) to compare time to biochemical recurrence (PSA ≥ 0.2), TTP and OS in patients treated with axitinib to patients treated with surgery alone. The Chi-square test will be used to compare the pStat3, LOX expression and MDSC density in patients treated with axitinib to patients treated with surgery alone. Descriptive statistics will be used to compare serum levels of VEGF-A, sVEGFR2, PDGF-AB and pSTAT3 at various timepoints during therapy.

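### Planned size (44 or 60) and duration (24 or 60 months) conflict, and the stated 80% power is for 22 evaluable men per group, not for the ITT analysis named as primary

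*Combined protocol and SAP*

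**What the plan says.** **Size.** The synopsis gives a sample size of 44, and its Statistical Considerations size the trial at 22 per group with no replacement allowance ("a one-sided t-test with type I error = 10% calculated using nQuery Advisor 6.01"). Section 3.3 also expects about 44 patients. Section 14.1.1 starts from the same 22: "With a sample of 22 patients per group, we will have 80% power to determine significance across groups". It then adds that "30 patients per group will be recruited according to an empirical replacement rate of 27" per cent. Section 14.2 refers to 60 patients.

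**Duration.** The synopsis estimates 24 months for the study. Section 14.2 expects accrual to take 60 months.

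**Analysis set.** Section 14.1.1 states: "The intention-to-treat analysis will be the primary analysis conducted to obtain unbiased comparisons between the treatment and control". Beyond that, "some as-treated subgroup analysis would also be investigated if necessary".

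**Replacement.** Section 6.5 is the only place that says who is replaced: "patients will be replaced if they do not receive at least 75% of the planned treatment with axitinib in the first cycle of therapy", which it equates to 21 of the 28 planned days. Section 6.1.1 says of the other arm: "In patients on the control arm, no systemic therapy will be instituted". No section says whether a replaced man stays in the ITT set. Section 6.4 says that men who stop study treatment for reasons other than progression "will continue to have PSA measurements every 24 weeks", and sections 7.0 and 7.1 also keep men removed for toxicity in follow-up.

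**The concern.** A reader needs two things from a sample-size section: how many patients will be randomised, and what power the primary analysis has at that number. The current text gives two answers to the first and none to the second.

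The 80% is for 22 men per group who all show the full treatment effect. Recruiting 30 to end with 22 is the logic of an evaluable-patient analysis. The named primary analysis is ITT, which by convention keeps every randomised man, including axitinib men who took too little drug. Keeping them raises the number analysed and may also shrink the average difference. These two effects pull power in opposite directions, so the ITT power could lie on either side of 80%. The plan should say which side it expects, and on what assumption.

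**Working it through.** **Inputs from section 14.1.1:** control mean 3.13, axitinib mean 2.19, common SD 1.43, one-sided t-test at 10%, 22 per group, 27% replacement, 30 per group. **Assumption, not in the documents:** the share of the 0.94 effect kept by under-treated men, varied from 0 to 100%.

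**1. Reproduce the plan's power.** The difference is 3.13 − 2.19 = 0.94. With n per group, the noncentrality is 0.94 / (1.43 × √(2/n)).
- n = 22: 0.94 / (1.43 × √(2/22)) = 2.18 on 42 df, giving power 81.0%. The stated 80% is reproduced.
- The same design tested two-sided at 10% gives 69.1%, so the one-sided reading is the one used.

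**2. Reproduce the 30 per group.** 22 / (1 − 0.27) = 22 / 0.73 = 30.1. Multiplying up instead gives 22 × 1.27 = 27.9, which does not lead to 30. In reverse, 30 × 0.73 = 21.9, and 8/30 = 26.7%. The inflation therefore treats about 8 men per group as not counting and 22 as remaining. The text does not say this outright; it is inferred from the arithmetic.

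**3. ITT power at 60 (30 v 30).**
- No dilution: 0.94 / (1.43 × √(2/30)) = 2.55 on 58 df, power 89.4%.
- 8 of the 30 axitinib men are under-treated and kept. The average difference becomes 0.94 × (22 + 8 × share kept) / 30. Power is from simulation with the pooled t-test:

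| Effect kept by the 8 men | Average difference | Power |
|---|---|---|
| 0% | 0.69 | 71% |
| 42% | 0.79 | 80% |
| 50% | 0.81 | 82% |
| 100% | 0.94 | 89% |

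- Fewer under-treated men, none of whom keep any effect: 79% with 5 of 30, 84% with 3 of 30.
- If the whole 27% were men without node tissue in both arms, 22 v 22 would remain and the stated figure would be right (81%).

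**4. ITT power at 44 (22 v 22, all kept).** It is 81.0% at full effect. If 27% of axitinib men keep no effect, the difference is 0.73 × 0.94 = 0.686. Power is then 61.6% with the SD held at 1.43, or about 60% once the extra variance from mixing treated and under-treated men is included. At 44 there is almost no margin above 80%, so even modest dilution takes power below it.

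**5. Duration.** Section 14.2 implies 60/60 = 1 patient per month. At that rate even 44 patients would take 44 months, so the synopsis's 24 months fits neither total.

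**The case against.** The best defence is that the analysis set is already specified. ITT is named as primary, as-treated analysis is additional, no passage drops replaced men, and men who stop axitinib stay in follow-up. The two statistical sections also agree on 60, so 44 may simply be text that was not updated. And 30 v 30 gives 89% undiluted, so the allowance may be ample.

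Much of this stands, and it rules out three stronger readings that a reader might infer:

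- *That the trial is underpowered at 60.* The documents do not show this. The 71% figure needs all 8 men to be under-treated axitinib patients who keep none of the effect, whereas section 6.5 replaces anyone below 21 of 28 days. Power reaches 80% once those men keep about 42% of the effect.
- *That replacement biases the comparison.* If replaced men were removed, only the axitinib arm would lose patients. The plan does not say they are removed, and naming ITT points the other way. This is a misreading to guard against, not a bias in the plan as written.
- *That a 27% allowance in both arms contradicts an axitinib-only rule.* Controls cannot meet the section 6.5 criterion. But if replacements enter through the balanced randomisation, about 30 per arm are needed to obtain about 22 adequately treated axitinib men, and the two statements agree. The plan neither states nor excludes this.

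The defence does not remove the conflict over N and duration, and it does not supply a power for the ITT set. If ITT means everyone, the stated 80% is not the power of the primary analysis.

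**Conclusion.** The point holds as an inconsistency in planned size and duration, together with a power statement for a set other than the primary one. It should be fixed, but it does not show the design to be unsound.

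The conflicts of 44 v 60 patients and 24 v 60 months are plain on the page and need no assumption. The power mismatch rests on reading 22/0.73 as an evaluable-patient inflation, which the arithmetic supports closely. How much it matters depends on two things the plan leaves unstated: what the 27% consists of in each arm, and how much effect under-treated men keep. Across the cases above, ITT power runs from 71% to 89% at 60. At 44 it runs from about 60–62% to 81%. The choice of N therefore matters more than the dilution question: 60 may well be adequate, while 44 meets the 80% target only with little or no dilution.

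**What to change.** 1. Give one N and one study duration throughout, reconciling the synopsis (sample size, duration and Statistical Considerations), section 3.3, section 14.1.1 and section 14.2.
2. In section 14.1.1, restate the power for the ITT set at that N. Give the make-up of the 27% by arm and the effect assumed to be kept by under-treated men. This needs no further enrolment.
3. In sections 6.5 and 14.1.1, state that replacement means additional accrual through the randomisation, that replaced men with node tissue stay in their assigned arm in the primary ITT analysis, and that the set receiving at least 75% of planned axitinib is the secondary as-treated analysis.

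The cost is a short text amendment, with no new procedures and no patients added by the amendment itself. The tissue comes from the node dissection already planned. The one drawback is that the restated power may look less favourable than 80%.

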6.6 Supportive Care and Other Concomitant Therapy

6.6.1 Investigational Therapy

No other investigational treatment may be given while the patient is on study.

6.6.2 Supportive Care

Appropriate antibiotics, blood products, antiemetics, fluids, electrolytes and general supportive care are to be used as necessary.

6.6.3 Concomitant Medications

Palliative and supportive care for disease-related symptoms, including pain medications, is permitted. Patients may receive loperamide or other medications for treatment or prophylaxis of potential diarrhea. Specific guidelines for managing diarrhea are noted in Appendix C. Anti-inflammatory or narcotic analgesics may be offered as needed. Patients with fever or infection may undergo diagnostic tests and treated with antibiotics as appropriate and may receive therapeutic colony-stimulating factors as appropriate. Erythropoietic agents such as epoetin or darbepoetin may be used at the discretion of the treating physician. Packed red blood cell and platelet transfusions should be administered as clinically indicated. Low-dose oral steroids (defined as ≤ 5 mg per day prednisone or equivalent), short course of oral steroids (defined as < 5 consecutive days or topical or inhaled steroids at any dose) may be taken during the study.

Patients who need to be on anticoagulant therapy during treatment with axitinib should be treated with low molecular weight heparin as the preferred therapy. The administration of coumadin or other coumarin derivatives is not allowed due to the possibility of inhibition of CYP1A2-mediated metabolism of coumadin by axitinib and resultant effects on coagulation parameters.

In vitro studies with human liver microenzymes and recombinant CYP enzymes indicated that axitinib metabolism was primarily mediated by the drug-metabolizing enzyme CYP3A, and to a lesser extent by CYP1A2. Additionally, the drug also undergoes N-glucuronidation in liver microsomes of some species. Clinically, there is likelihood that axitinib plasma concentrations may be increased in the presence of co-administered potent inhibitors of the CYP3A and glucuronosyltransferase enzymes. In a healthy volunteer study, ketoconazole, a potent CYP3A inhibitor, produced a 2-fold increase in plasma exposure and a 1.5-fold increase in peak plasma concentration of axitinib. Therefore a potential exists for drug-drug interactions with CYP3A inhibitors such as grapefruit juice, ketoconazole, miconazole, itraconazole, erythromycin, clarithromycin, telithromycin, verapamil, indinavir, saquinavir, ritonavir, nelfinavir, lopinavir, atazanavir, amprenavir, fosamprenavir and delavirdine. Treatment is prohibited in patients receiving axitinib in combination with these and other potent CYP3A inhibitors until appropriate clinical drug interaction studies are performed.

Axitinib metabolism may be induced in patients taking CYP3A4 or CYP1A2 inducers (carbamazepine, dexamethasone, felbamate, omeprazole, phenobarbital, amobarbital, phenytoin, primidone, rifabutin, rifampin, nevirapine, and St John's wort) and this may reduce axitinib plasma concentrations. Patients who require concomitant treatment with potent CYP3A4 or CYP1A2 inducers are not eligible for the study. Since CYP1A2 is also known to be induced in chronic smokers, there is likelihood that axitinib plasma concentrations may be reduced in these individuals. (Note: these patients are not excluded from enrolment, however.)

The ability of axitinib to increase concentrations of coadministered drugs was also investigated in studies with human liver microsomes. At expected therapeutic plasma concentrations (0.01 to 1.0 μ g/mL),

axitinib appears most likely to inhibit the drug metabolizing enzymes CYP1A2 and CYP2C8, 2 enzymes not frequently observed as predominant drug metabolizing enzymes. Theophylline, and tacrine are among the few drugs whose plasma concentrations are likely to be increased by axitinib.

Axitinib is highly bound to proteins in human plasma (99.5% bound at concentrations between 0.2 to 20 $\mu\text{g/mL}$). Therefore, drug interactions with other agents that are also highly bound to plasma proteins are a possibility.

Patients who need to be on chronic antacid therapy with histamine H_2 antagonists (eg, cimetidine [Tagamet[®]], famotidine [Pepcid[®]], nizatidine [Axit[®]], ranitidine [Zantac[®]]), proton-pump inhibitors (eg, lansoprazole [Prevacid[®]], rabeprazole [Aciphex[®]], pantoprazole [Protonix[®]], and esomeprazole [Nexium[®]]), or locally acting antacids (eg, Maalox[®], Milk of Magnesia[®], Amphojel[®]) should stagger the timing of their axitinib and antacid dosing. Patients should avoid use of antacids for 2 hours before through 2 hours after taking axitinib tablets. Note, however, that patients taking the proton-pump inhibitor omeprazole (Prilosec[®]) are not eligible for this study and that patients should not use omeprazole while taking axitinib tablets because omeprazole is a CYP1A2 inducer.

Axitinib is not likely to have drug-drug interactions with commonly used antihypertensive agents belonging to the class of ACE inhibitors including angiotensin II receptor antagonists (enalapril, captopril, losartan, vasartan), beta-blockers (atenolol, metoprolol, labetalol), or diuretics (hydrochlorothiazide, furosemide). Within the class of calcium channel blockers, verapamil, and to a lesser extent nifedipine, nicardipine, and diltiazem have a potential for increasing plasma A-013736 plasma concentrations, due to CYP3A inhibition and should not be used as first choice in antihypertensive treatment. Other calcium channel blockers (amlodipine, bepridil, felodipine) are less likely to raise axitinib plasma levels.

The above information is based on preclinical data from studies using human and animal metabolizing enzyme systems.

All concomitant medications and blood products, as well as interventions (eg, analgesic use or paracentesis) received by patients from the first dose of axitinib until the end of study visit should be recorded on the CRF. Furthermore, all concomitant medications being used at the time of study entry should be reviewed by the prescribing MD and protocol nurse to ensure eligibility and exclusion criteria for the study are not violated. All changes to concomitant medications during the course of therapy will additionally be reviewed by the prescribing MD and protocol nurse, as well, to ensure that prohibited medications are avoided.

